Appendix 1 – ECOG Performance Status

[figure not shown]
Appendix 2 – Cosmesis Score Sheet

Appendix 3 – Breast-Q Reconstruction Module (Post-Operative) 2.0

Appendix 4 – Breast-Q Mastectomy Module (Post-Operative) 2.0

List of Abbreviations

3DCRT	3-D Conformal Radiation Therapy
AE	Adverse Event/Adverse Experience
CBCT	Cone Beam CT
CFR	Code of Federal Regulations
CRF	Case Report Form
CTV	Clinical Target Volume
DSMB	Data and Safety Monitoring Board
FDA	Food and Drug Administration
GCP	Good Clinical Practice
HIPAA	Health Insurance Portability and Accountability Act
IBTR	Ipsilateral breast tumor recurrence
IMRT	Intensity Modulated Radiation Therapy
IRB	Institutional Review Board
MRI	Magnetic Resonance Imaging
PHI	Protected Health Information
PI	Principal Investigator
PTV	Planning Target Volume
QOL	Quality of Life
RBE	Relative biologic effectiveness
RT	Radiation Therapy
SAE	Serious Adverse Event/Serious Adverse Experience
SOP	Standard Operating Procedure
XRT	X-ray Radiation Therapy

Study Design: This is an open label phase II randomized controlled trial to determine the safety of 15 fraction vs 25 fraction pencil beam scanning proton radiotherapy after mastectomy in patients requiring regional nodal irradiation. Proton therapy is recognized as a standard option for the delivery of radiotherapy for breast cancer.

1.0 Background

1.1 Benefits and Risks of Adjuvant Radiotherapy

Postmastectomy radiotherapy to the chest wall and regional lymph nodes after mastectomy have been shown to result in improvement in rates of recurrence and survival for women with early stage and locally-advanced breast cancer[1]. Despite the oncologic benefits of radiotherapy, however, concerns have been raised regarding the attending toxicity of photon radiotherapy. Data demonstrating late cardiovascular toxicity, particularly for women with left-sided tumors, and risk of secondary malignancy have garnered particular attention in recent years,[2] and these toxicities have been shown to partially offset the cause-specific survival benefit of adjuvant radiotherapy[1, 3].

Cardiovascular toxicity has been studied in great detail and appears to be primarily mediated by a vascular etiology, likely with macro- and microvascular contributions. Correa and colleagues[4] demonstrated a likelihood of left anterior descending artery (LAD) stenosis for women treated with adjuvant radiotherapy for breast cancer in excess of what would be expected for the general population, providing indirect evidence of radiation-mediated coronary artery disease. Darby and co-authors[3] found that the risk of major coronary events (myocardial infarction, coronary revascularization, or death from ischemic heart disease) was related to the mean heart dose and not the LAD, suggesting a microvascular etiology. Notably in that study the increase in cardiac toxicity began within the first 5 years after radiotherapy. Cardiovascular toxicity is likely multifactorial, and multiple dose-volume relationships are important in determining risk of subsequent cardiac disease, including dose to the LAD, heart (mean heart dose and volumetric parameters such as V₂₅) and left ventricle[5].

Adjuvant radiotherapy for breast cancer has also been associated with an elevated risk of developing a secondary malignancy[1]. Specifically, radiotherapy is associated with increased risk of developing and dying from ipsilateral lung cancer[1, 6]. Radiotherapy is also associated with increased risk of developing esophageal and contralateral breast carcinoma[1]. This is a result of inadvertent and unnecessary dose delivered to normal organs adjacent to disease targets. Radiotherapy to the axillary and supraclavicular lymph nodes increases the risk of lymphedema following axillary surgery.[7] Radiotherapy to the breast and chest wall is also associated with breast fibrosis, breast shrinkage, worsening of cosmesis, and arm and shoulder pain.[8, 9] In patients who undergo mastectomy with implant based reconstruction, postmastectomy radiotherapy is associated with higher rates of complication including capsular contracture, unplanned re-operation, and reconstruction failure.[10]

In summary, although adjuvant radiotherapy for breast cancer improves locoregional control and survival, there is strong rationale for the evaluation of novel techniques that reduce unnecessary exposure to normal tissue and novel dose and fractionation regimens which may improve the therapeutic ratio.

1.2 Rationale for Proton Therapy in Breast Cancer

Relative to photons, protons have fundamental physical advantages in the treatment of tumors adjacent to radiosensitive normal structures. By exploiting the Bragg peak of proton beams, clinicians are able to achieve a dose distribution to target tissues similar or better to that accomplished with photons, while reducing unintended dose to nearby normal structures[11, 12]. Thus, interest in the possible benefits of breast cancer radiotherapy with protons is emerging, with hopes of being able to maintain or improve the locoregional control and cause-specific survival with the addition of photon radiation, while reducing toxicity.

MacDonald et al [13] recently published early outcomes for a small cohort of 12 patients treated with proton radiotherapy following mastectomy. All patients received chest wall irradiation and eleven received radiotherapy to the supraclavicular, level 3, and internal mammary lymph node chains. Five of the 12 women had permanent implants at the time of radiotherapy. Nine patients had grade 2 skin toxicity and 3 patients had grade 1 skin toxicity. There was no \geq grade 3 skin toxicity reported. During treatment 6 patients experienced grade 1 fatigue, 5 patients experienced grade 2 fatigue, and there was one incident of grade 3 fatigue. By 4 weeks follow-up fatigue had completed resolved in all but 1 patient who continued to have grade 1 fatigue. There were no reported cases of pneumonitis. The average mean dose to the heart was 0.44 Gy and the average mean V20 of the lung was 12.7%. Cuaron et al. recently reported the results of treatment of the largest cohort of patients treated with proton therapy for breast cancer.[14] Four patients were treated after lumpectomy, 24 after mastectomy (including 14 patients with implant reconstruction and 1 patient with autologous reconstruction) and 2 patients received proton therapy after wide local excision of a chest wall recurrence. Grade 2 dermatitis occurred in 20 patients (71.4%), 8 of whom (28.6%) also experienced moist desquamation. Grade 2 esophagitis was observed in 8 patients (28.6%). There was 1 grade 3 reconstructive complication. The median mean heart dose was 0.88Gy and the median V20 of the ipsilateral lung was 16.5%. This early data suggests that post-mastectomy proton therapy is feasible and associated with reduced dose to the heart and lung, warranting further study.

The work of MacDonald and colleagues was performed using passively scattered protons. A concern with this technique is the high entrance skin dose which may be associated with higher skin toxicity.[15] Scanning beam proton therapy, the technique proposed in this study, offers potential advantages over passively scattered protons including increased conformality with less unintended dose to normal tissues, including the skin.[16] However, this technique is also potentially more sensitive to uncertainties including interfractional as well as intrafractional motion which must be taken into account in treatment delivery. Rigorous clinical studies of scanning beam proton therapy are needed to determine the disease control and toxicity outcomes with this technique and to determine whether the physical dose advantages of proton therapy translate to substantial and lasting improvements in patient outcome.

1.3 Rationale for Hypofractionation in Breast Cancer

The optimal dose and fractionation regimen for postmastectomy radiotherapy remains unknown. The linear-quadratic formula model has emerged as the preferred method of predicting the relationship between fraction size and tissue response of varying radiotherapy regimens. Its origins stem from what has been described as a two-component survival curve for mammalian cells represented by the curvilinear dose-response curve for the log of cell survival.[17] In it, the biologically effective dose (BED) of a given fractionation regimen is related to the α/β ratio in the following equation,

where α represents the \log_e of the cells killed per gray and β is the \log_e of the cells killed per gray squared:

$$\text{BED} = nd(1 + d/\alpha/\beta)$$

d = dose per fraction
n = # of identical fractions

The ratio of α/β is the dose at which the linear and quadratic components of cell killing are the same. In general, early-responding tissues such as skin desquamation have a high ratio whereas late-responding tissues such as dermal contraction have a low ratio and are very sensitive to increases in fraction size.[18] Therefore, patients treated by Macdonald and colleagues and Cuaron and colleagues generally received 50.4 Gy (relative biological effectiveness [RBE]) to the chest wall and 45-50.4 Gy (RBE) to the regional lymph nodes in 1.8 Gy (RBE) fractions using an RBE value of 1.1.[14, 19]

Emerging evidence, however, suggests that the α/β ratio of breast cancer may be low and more in line with that of late responding tissues and therefore breast cancer patients may not benefit from prolonged fractionation regimens.[20, 21] Indeed, the most robust data to date suggesting this relationship has come from the UK Standardization of Breast Radiotherapy (START) trials, two modern breast cancer randomized controlled trials examining various fractionation regimens that have recently been reported with 10-year follow-up. In START-A, a regimen of 50Gy in 25 fractions to the whole breast over 5 weeks was compared with 41.6Gy or 39 Gy in 13 fractions over 5 weeks. There was no significant difference in local-regional relapse between the 41.6Gy and 50Gy regimens (6.3% vs 7.4%, p=0.65) or the 39Gy and 50Gy regimens (8.8 vs 7.4%, p=0.41).[9] Moderate or marked breast induration, telangiectasia, and breast edema was less common in the 39Gy group compared with the 50Gy group, and rates of these toxicities were no different between the 41.6Gy and 50Gy groups. The treatments in each arm were given over the same time period, enabling an estimate of sensitivity of breast cancer to changes in fraction size that was not confounded by differences in treatment time. An α/β ratio for local-regional relapse of breast cancer was determined from a meta-analysis of START-A and the START pilot trial (349 events, 3646 women) as 3.5 Gy (95% CI 1.2-5.7). The α/β ratio for normal tissue toxicity endpoints included 3.5Gy (95% CI 0.7-6.4) for breast shrinkage, 4Gy (2.3-5.6) for breast induration, 3.8Gy (1.8-5.7) for telangiectasia, and 4.7 Gy (2.4-7.0) for breast edema, suggesting that normal tissue toxicity may not be reduced and may even be increased when breast cancer radiotherapy fractionation regimens are prolonged with small daily fractions.

Further evidence suggesting hypofractionated regimens may be attractive for breast cancer came from the START-B clinical trial, in which 50Gy in 25 fractions over 5 weeks was compared with 40Gy in 15 fractions over 3 weeks. There was no difference in local-regional relapse at 10 years between 40Gy and 50Gy groups, (4.3% vs 5.5%, p=0.2) but breast shrinkage, telangiectasia, and breast edema were significantly less common with the shorter fractionation regimen. These data are consistent with the results of the Canadian hypofractionation trial which compared 42.5Gy in 16 fractions in 3.2 weeks to 50Gy in 25 fractions over 5 weeks, and suggest that the use of smaller fractions is of no benefit in terms of tumor control or reduction in toxicity, at least in the doses used in these studies, and may potentially be deleterious.[9, 22]. Interestingly, if one applies an α/β ratio for both normal tissue toxicity and tumor control of 3.5 from START-A, the 40Gy regimen from START-B is equivalent to 44.9Gy in 2 Gy fractions. This may imply

that differences in overall treatment time of a course of radiation therapy may be more important than originally thought.[23, 24].

Only a small minority of patients treated on the START-A and START-B clinical trials had undergone mastectomy or received regional nodal irradiation and none underwent immediate reconstruction. Therefore in North America, 1.8-2 Gy fraction size remains the “preferred” dose in these settings.(NCCN 2014) More data is needed to determine whether patients treated to the chest wall and regional nodes might also benefit from hypofractionated approaches. Moreover, it will be critical to understand whether hypofractionated radiotherapy is feasible in the setting of immediate implant based reconstruction. Finally, there is no data available presently on the role of hypofractionation for breast cancer with scanning beam proton therapy.[13]

Although the use of proton therapy for breast cancer is still in early development, concerns regarding proton therapy have primarily been related to costs, rather than technical feasibility in the clinic. Proton therapy departments are more expensive to build as they require huge accelerators to deliver the beam. Although protons are considered more expensive than conventional forms of radiation, cost-benefit studies have suggested cost-effectiveness in the long term due to decreased long term toxicity.[25, 26] An important driver of cost of both photon and proton radiotherapy is the number of treatments delivered to individual patients. Studies are needed to evaluate whether equivalent or improved outcomes can be achieved with shorter courses of therapy.

The overlying hypothesis of this study is that the low α/β of breast cancer can be exploited with a carefully designed hypofractionated proton therapy regimen in the post-mastectomy setting to further optimize the therapeutic ratio, improve patient convenience, and reduce cost.

2.0 Goals

2.1 Primary

2.1.2 To determine whether the 24 month complication rate (defined as grade 3 or greater late adverse events; and unplanned surgical intervention in patients who undergo mastectomy with reconstruction) of 15 fraction chest wall and regional node pencil beam scanning proton radiotherapy is acceptable relative to 25 fraction chest wall and regional nodal pencil beam scanning proton radiotherapy and worthy of further investigation.

2.2 Secondary

2.2.1 To evaluate acute and late toxicity

2.2.2 To evaluate the rate of reconstruction failure (defined as loss of the tissue expander or implant with the inability to replace it resulting in no final reconstruction or conversion to autologous reconstruction or unplanned revision with the addition of autologous reconstruction).[27, 28]

2.2.3 To determine the 5-year locoregional control, disease free survival and overall survival

- 2.24 To evaluate fatigue, arm function, and other patient reported outcomes
- 2.25 To evaluate clinical features, treatment technique, dose-volume parameters, histologic and genetic variants associated with fair and poor cosmetic outcome or unplanned surgical intervention.
- 2.26 To compare echocardiographic changes, including left ventricular strain pattern, between fractionation regimens

3.0 Patient Eligibility

3.1 Inclusion Criteria

- 3.12 Age \geq 18 years
- 3.13 Histologic confirmation of breast cancer resected by mastectomy with or without immediate reconstruction and chest wall and regional nodal irradiation planned.
- 3.14 pStage T1-T4N0-N3M0 or ypStage T0-4N0-N3M0
Note: The axilla must be staged by sentinel node biopsy alone, sentinel node biopsy followed by axillary node dissection, or axillary lymph node dissection alone
- 3.15 ECOG Performance Status (PS) 0 to 2. (Appendix I).
- 3.17 Radiotherapy must begin within 12 weeks of last surgery (breast or axilla) or last chemotherapy.
Note: Breast implants and expanders allowed
- 3.18 Able to and provides IRB approved study specific written informed consent
- 3.19a Ability to complete questionnaire (s) by themselves or with assistance
- 3.19b Able to complete all mandatory tests listed in section 4.0
- 3.19c Willing to return to enrolling institution for follow-up (during the active monitoring phase of the study)
- 3.19d Willing to provide tissue and blood samples for correlative research purposes.
- 3.19e Rochester and Arizona patients: Willing to sign consent onto the Mayo Clinic Radiotherapy Patient Outcomes Registry and Biobanking study, IRB number 15-000136
- 3.30 Rochester patients: Willing to sign consent onto Evaluation of cardiac function in patients undergoing proton beam or photon radiotherapy, IRB number 15-007443

3.2 Exclusion Criteria

- 3.21 Medical contraindication to receipt of radiotherapy.
- 3.22 Severe active co-morbid systemic illnesses or other severe concurrent disease which, in the judgment of the investigator, would make the patient inappropriate for entry into this study or interfere significantly with the proper assessment of safety and toxicity of the prescribed regimens.
- 3.23 Uncontrolled intercurrent illness including, but not limited to, ongoing or active infection, symptomatic congestive heart failure, unstable angina pectoris, cardiac arrhythmia, or psychiatric illness/social situations that would limit compliance with study requirements or providing informed consent.
- 3.24 Active systemic lupus or scleroderma.
- 3.25 Pregnancy or women of childbearing potential who are sexually active and not willing/able to use medically acceptable forms of contraception
- 3.26 Prior receipt of ipsilateral breast or chest wall radiation that would result in significant overlap of radiation therapy fields. Prior contralateral radiotherapy for breast cancer is allowed.
- 3.27 Positive margins after definitive surgery
- 3.28 History of non-breast malignancies (except for in situ cancers treated only by local excision and basal cell and squamous cell carcinomas of the skin) within 5 years prior study entry
- 3.29 Inflammatory breast cancer
- 3.29a Recurrent Breast Cancer
- 3.29b Boosts to the chest wall after mastectomy. Nodal boosts are allowed.

4.0 Test Schedule

Assessments, tests and procedures	Treatment			Observation ⁷
	Baseline ²	Last day of treatment (+/- 2 days)	12 weeks (+/- 8 weeks) post-radiation	12 months (+/- 3 month) post completion of radiotherapy, 24 months (+/- 3 months), 36 months (+/- 3 months), and at 5 years (+/- 3 months)
History and Physical exam (including breast assessment/exam) ¹	X	X	X	X
Mammogram	X ¹⁰			X ¹¹
Cosmesis ,QOL Outcome Assessment and Breast-Q ¹⁶ (see section 11.3 and Appendix)	X ¹³	X	X	X
Digital Photograph	X	X	X	X
Review of surgical specimen(s) to confirm eligibility	X ³			
Echocardiography ^{9, 14}	X ¹³			X ⁸
Radiation toxicity assessment (see section 10.4)	X	X	X	X
Serum pregnancy test	X ⁴			
Blood specimen ^{5, 17, R}	X ¹⁵	X	X	X ¹²
Surgical tumor specimen ^{6, 18, R}	X			

1. A general history & physical must be done \leq 8 weeks prior to registration. This should include an assessment of ECOG performance status (see Appendix I).

2. Following definitive surgical resection and adjuvant chemotherapy if indicated, prior to the start of radiation.
3. Outside pathology must be reviewed at the treating institution.
4. For women of childbearing potential only, must be within 7 days of radiotherapy
5. See section 14 for collection time and preparation of samples
6. See section 17 for collection time and preparation of samples
7. Patients that cannot come back to Mayo Rochester within the time constraints of the follow-up schedule; efforts to obtain outside records and send QOL's to be completed will occur, however the required items may not be captured.
8. Ideally 6-12 months post radiotherapy in HER2 positive patients treated with HER2 directed therapy and in patients treated with anthracycline as part of routine clinical care. Only followed for Echos 1 year post therapy.
9. Co-enrollment on IRB 15-007443 (echo protocol) is required in Rochester while open
10. Completed \leq 12 months prior to study entry
11. As clinically indicated
12. At 12 months post-treatment visit only to coincide with echocardiography.
13. Should be \geq 14 days since last chemotherapy
14. After closure of IRB 15-007443 (echo protocol) echocardiography tests will be performed only in left sided patients previously treated with anthracycline and/or HER2 directed systemic therapy. This correlative component will occur at Rochester Mayo only.
15. Baseline blood collection will be drawn through co-enrollment on IRB 15-000136 (Radiation Oncology Outcomes Registry and Biobanking Study).
16. Breast-Q forms to be completed by patient at Observation timepoints.
17. Post radiation blood specimen submission for Rochester site only.
18. Surgical tumor specimen for Rochester site only.

R. Research funded

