7.0 Protocol Treatment

Doses throughout will be prescribed in Gy (RBE). One Gy will be the equivalent of one Gy (RBE) for proton therapy for the purposes of the descriptions below. Radiation therapy must begin within 12 weeks of the last breast cancer surgery or the last dose of adjuvant chemotherapy and no sooner than 14 days since the last chemotherapy. The dose, schedule, and timing (neoadjuvant vs adjuvant) of chemotherapy and endocrine therapy are at the discretion of the treating oncologists. Concurrent cytotoxic chemotherapy with radiotherapy is not allowed. Use of anti-HER2 therapy during radiotherapy is permitted.

7.1 Radiation Therapy Arm 1

Patients who are randomized to arm 1 will receive conventionally fractionated radiotherapy in daily fractions to the chest wall plus regional nodal area CTV (with setup uncertainty analyses of 3-5mm perturbations along each translation axis and 3% beam range uncertainty). Boosts to the chest wall after mastectomy are not permitted but nodal boosts to sites of initial gross disease are allowed.

7.2 Radiation Therapy Arm 2

Patients who had a lumpectomy or mastectomy and are randomized to arm 2 will receive hypofractionated radiotherapy in daily fractions to the chest wall plus regional nodal area CTV (with setup uncertainty analyses of 3-5mm perturbations along each translation axis and 3% beam range uncertainty). Boosts to the chest wall after mastectomy are not permitted but nodal boosts to sites of initial gross disease are allowed.

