11.5 Cardiopulmonary function testing

11.5.1 Echocardiography is a noninvasive tool that enables the detection of cardiovascular disease as a result of radiotherapy. Echocardiography can detect pericardial disease, left ventricular systolic and diastolic dysfunction, coronary artery disease suggested by resting or stress-induced regional wall motion abnormalities, and valvular heart disease.[33] Furthermore, echocardiographic strain rate imaging, a measure of regional myocardial function, has previously been reported to detect subclinical decline in cardiac function in the anterior wall of patients treated with radiotherapy for left-sided breast cancer.[34] Echocardiography will be used to detect clinical or subclinical cardiovascular disease as a result of radiotherapy.

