- 16.626 *Regional recurrence incidence*: The regional breast cancer recurrence cumulative incidence will be estimated using a competing risks method (Gooley et al.) by treatment arm. The competing risks will be local/distant breast cancer recurrence and death.
- 16.627 *Distant recurrence incidence*: The distant breast cancer recurrence cumulative incidence will be estimated using a competing risks method (Gooley et al.) by treatment arm. The competing risks will be local/regional breast cancer recurrence and death.
- 16.628 *Disease-free survival*: DFS is defined as the time from registration until the time of disease recurrence or death due to any cause. The DFS will be estimated with a Kaplan-Meier estimator and curve by treatment arm. Estimates will be given for specific time points along with 95% CIs.
- 16.629 *Overall survival*: The OS will be estimated with a Kaplan-Meier estimator and curve by treatment arm. Estimates will be given for specific time points along with 95% CIs.
- 16.63 Exploratory Analyses: 2D and 3D strain parameters will be analyzed after radiotherapy compared to baseline and will be compared between patients undergoing conventional versus hypoofractionated radiotherapy. Continuous variable will be compared using unpaired t tests and nominal variables will be compared using contingency tables and Chi square analyses.
- 16.64 Correlative Analyses:

16.641 Cardiac toxicity

Cardiac toxicity remains an important late effect of radiotherapy for breast cancer.[3, 34, 37, 38] Echocardiography is a noninvasive tool that enables the detection of cardiovascular disease as a result of radiotherapy. Echocardiography can detect pericardial disease, left ventricular systolic and diastolic dysfunction, coronary artery disease suggested by resting or stress-induced regional wall motion abnormalities, and valvular heart disease.[33] Ideally, cardiac toxicity could be predicted prior to the onset of clinical symptoms to enable an earlier opportunity for risk stratification, surveillance, and preventative interventions that reduce risk. Echocardiographic strain rate imaging, a measure of regional myocardial function, has previously been reported to detect subclinical decline in cardiac function in the anterior wall of patients treated with radiotherapy for left-sided breast cancer.[34]

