Patients requiring regional nodal irradiation, including treatment of the internal mammary lymph nodes, are at highest risk of developing radiation induced late cardiac complications such as coronary artery disease and myocardial infarction.[39] This is a result of a higher mean dose to the heart when dose the internal mammary lymph nodes are targeted.[3] Furthermore, many high risk patients are exposed to anthracyclines and HER2 directed therapies such as trastuzumab and pertuzumab which are also associated with cardiovascular toxicities [40]. Therefore, assessment of therapy-induced cardiac toxicity will be performed as outlined in section 4.0.

Cardiac imaging modalities have limitations such as cost and operator-dependency. In contrast, serum biomarkers are operator-independent and are a potentially lower cost, non-invasive means of predicting cardiac toxicity. In one prospective study of women undergoing adjuvant radiotherapy for breast cancer, mean cardiac troponin I (TnI) levels, a highly sensitive marker of cardiac damage, were significantly elevated after photon radiotherapy in left-sided patients compared to baseline, but not in right-sided patients.[34] However, other studies have not shown cardiac troponins to consistently be of clinical utility in this setting.[41, 42]. The natriuretic peptide N-terminal pro-B-type natriuretic peptide (NT-proBNP) has also been shown to be elevated in left-sided breast cancer patients after photon radiotherapy for breast cancer.[42] Similar to the case of cardiac troponins, results have been mixed and inconsistent.[41] There is no information available regarding the effects of scanning beam proton radiotherapy for breast cancer on these cardiac biomarkers. Blood will be drawn according to the schedule in section 4.0 to assess cardiac troponins and natriuretic peptides. Changes across time will be evaluated. In addition, blood will be stored for future testing of emerging biomarkers of radiation induced cardiac toxicity.

16.643 Molecular and Genomic Predictors of Fibrosis and Reconstruction Toxicity

Predictors of fibrosis and reconstruction failure are poorly understood. If a subset of patients at high risk of complications could be identified, their treatment could be personalized. Factors previously associated with worsened cosmesis after breast conserving therapy include inferior tumor location, large excision volume,

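### The before/after strain change in section 16.63 mixes radiotherapy with drug effects arising between the two echoes, mainly from anti-HER2 therapy, so it cannot be attributed to radiotherapy as section 11.5.1 implies

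*Combined protocol and SAP*

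**What the plan says.** **Purpose.** Section 11.5.1 states: "Echocardiography will be used to detect clinical or subclinical cardiovascular disease as a result of radiotherapy".

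**Analysis.** Section 16.63 (exploratory) says that "2D and 3D strain parameters will be analyzed after radiotherapy compared to baseline", and that strain will also be compared between the two fractionation groups. It names unpaired t tests and chi-square tests. It has no covariate, stratum or subgroup for systemic therapy. Goal 2.26 is the comparison between regimens.

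**Who has the follow-up echo.** Footnote 8 to section 4.0 places it ideally 6 to 12 months after radiotherapy "in HER2 positive patients treated with HER2 directed therapy and in patients treated with anthracycline as part of routine clinical care", and adds: "Only followed for Echos 1 year post therapy". Footnote 9 says: "Co-enrollment on IRB 15-007443 (echo protocol) is required in Rochester while open". Once that protocol closes, footnote 14 says "echocardiography tests will be performed only in left sided patients previously treated with anthracycline and/or HER2 directed systemic therapy", at Rochester only.

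**Systemic therapy.** Section 7.0 states: "Use of anti-HER2 therapy during radiotherapy is permitted". Concurrent cytotoxic chemotherapy is not allowed. Baseline is after surgery and any adjuvant chemotherapy (footnote 2), and the baseline echo should be at least 14 days after the last chemotherapy (footnote 13). No such interval is given for anti-HER2 therapy. Section 16.641 notes that "many high risk patients are exposed to anthracyclines and HER2 directed therapies such as trastuzumab and pertuzumab which are also associated with cardiovascular toxicities".

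**Balance.** Section 5.1 balances randomisation on immediate reconstruction only.

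**The concern.** The plan names the competing cause in 16.641, directs follow-up echoes to the women exposed to it, and lets one class of these drugs continue across the interval being measured. Yet 11.5.1 assigns the findings to radiotherapy, and 16.63 has no means of separating the two.

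At stake is what the trial may say about proton radiotherapy and the heart. A fall in strain caused by continuing anti-HER2 therapy could be described as radiation injury. A smaller issue is that drug exposure is neither balanced nor adjusted for, so a chance imbalance adds some noise to the comparison of arms.

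**Working it through.** The documents state no sample size, power or effect size for strain, so there is no planned figure to reproduce. The sizes below are illustrations under stated assumptions.

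**1. What the before/after mean estimates.** Let R be the radiotherapy effect, H a drug effect that arises between the two echoes, and f the share of echo women who have it. Then

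mean change = R + f × H.

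Every woman in both arms is irradiated (7.31, 7.32). One group measured twice cannot separate R from f × H.

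**2. Which drugs enter H.** An anthracycline effect already present at baseline drops out of the change, because the baseline echo follows chemotherapy by at least 14 days. Only a later-emerging effect enters. Anti-HER2 therapy may continue during radiotherapy, so its effect can accrue between the echoes. It is the main component.

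**3. How often a drug effect alone gives a significant change.** Assumptions, none from the documents: R = 0; f = 0.40; H = 0.25, 0.50 or 0.75 SD, where SD is that of the change over all echo women; n = 20 or 30 women with both echoes; paired t test, two-sided 5%. The test is paired because before and after come from the same women; 16.63 names only unpaired t tests. Noncentrality = f × H × √n, with √20 = 4.472 and √30 = 5.477.

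| H | f × H | n = 20: noncentrality, rejection | n = 30: noncentrality, rejection |
|---|---|---|---|
| 0.25 | 0.10 | 0.447, 7% | 0.548, 8% |
| 0.50 | 0.20 | 0.894, 14% | 1.095, 19% |
| 0.75 | 0.30 | 1.342, 25% | 1.643, 36% |

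The nominal rate is 5%. If SD means the SD among women with the same drug status, the overall SD becomes √(1 + 0.4 × 0.6 × H²), which is 1.065 at H = 0.75. The bottom row then falls to 22% and 32%.

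**4. Sensitivity to f.** By normal approximation, with H = 0.3 to 0.5 SD and n = 20 to 40, the rate is 6% to 12% at f = 0.25, 10% to 34% at f = 0.5 and 27% to 89% at f = 1. The share affected drives the result, and the documents do not give it.

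**5. The comparison of arms.** Randomisation makes the expected drug contribution equal in the two arms. With m women per arm and 40% on anti-HER2 therapy, the SD of the difference in that share is √(2 × 0.4 × 0.6 / m): 0.219 at m = 10 and 0.179 at m = 15. An imbalance of 20 points or more occurs with probability 49% and 35%. A one-SD imbalance with H = 0.5 SD moves the arm difference by 0.5 × 0.219 = 0.11 SD or 0.5 × 0.179 = 0.09 SD. The standard error of that difference, √(2 / m), is 0.45 or 0.37 SD. The shift is about a quarter of a standard error in both cases.

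**The case against.** **The plan does not say that drug effects will be reported as radiation damage.** The wording in 16.63 describes timing, and 16.641 goes on to describe the echo work as assessing cardiac toxicity from therapy in general. This stands in part: the attribution is in one sentence of 11.5.1. But 16.63 offers nothing to qualify that sentence.

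**The stated goal is the randomised comparison.** This stands. A reader might infer that the arm comparison is confounded as well, or that an imbalance would be read as a fractionation effect. The documents do not support that. The comparison is unbiased in expectation, chance imbalance is already within the test's error rate, and step 5 shows the typical shift is small against the standard error. Not balancing a trial of 72 evaluable patients on drug exposure is not a defect.

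**Anthracycline should not be grouped with anti-HER2 therapy.** This largely stands, for the reason in step 2.

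**The echo population may be wider than footnote 8 suggests.** Footnote 8 can be read as a timing preference. The restriction in footnote 14 applies only after IRB 15-007443 closes, and that protocol's schedule is not in the documents. So it cannot be said that all echo women were drug-exposed. If unexposed women have paired echoes they would be a useful contrast, but 16.63 does not plan to use them.

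**The analysis is exploratory.** This stands and limits the weight of the point.

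**Conclusion.** The point holds for the before/after strain change: as written, it cannot be attributed to radiotherapy. It does not hold against goal 2.26.

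The size rests wholly on assumptions. With 40% of echo women affected by a 0.25 to 0.75 SD drug shift and no radiotherapy effect, a paired 5% test declares a change in about 7% to 25% of trials with 20 women and 8% to 36% with 30. A reader might apply the same shifts to every echo woman and reach 19% to 89% with 20 women and 26% to 98% with 30. That requires all of them to have a drug effect emerging between the echoes. Nothing in the documents shows this: even under footnote 14, prior anthracycline alone qualifies a woman, and its early effect is already in her baseline.

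The point is minor. It limits what may be concluded about cardiac effects and does not touch the primary endpoint.

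**What to change.** 1. In 16.63, make the between-arm difference in strain change the main strain result, from a model that includes HER2-directed therapy (yes/no) and prior anthracycline (yes/no). Take both from the neoadjuvant and adjuvant therapy forms in 18.1. Interpret the result as a fractionation effect only. Both arms receive proton radiotherapy, so it says nothing about radiotherapy against none.
2. Label the before/after change as change under combined treatment, show it descriptively by HER2-directed therapy, and reword the sentence in 11.5.1 to match.

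**Cost.** No visit, test or treatment changes. The model spends two degrees of freedom in a small exploratory subset, and the before/after claim becomes more modest. The forms also need a check: 18.1 lists the systemic-therapy forms under initial material, and the follow-up table has none. It is therefore not shown that anti-HER2 exposure is fully captured, or that its dates relative to each echo are collected.
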